## 12.0 Regulatory Requirements

**Role of Collaborating Institutions in the Oversight and Conduct of Human Subjects Research.** The proposed study is a collaboration between UIC (primary institution), Pennsylvania State University (PSU), Washington University in St. Louis (WashU), and Stanford University. All study participants are patients of UI Health, and the UIC IRB is the IRB of record. [name], MD, PhD, and [name], MD, PhD, both of UIC are co-principal investigators. Also, at UIC, [name], PhD brings expertise on machine learning and AI development, and [name], MD, MPH provides expertise on implementation and evaluation of digital health behavioral interventions in disadvantaged populations of diverse racial and ethnic backgrounds. As the Study Physician, [name] (psychiatrist) oversees the clinical aspects of the study, involving patient recruitment and safety, and as needed, coordinate care with participants' PCP. For more details, see Section 7. [name], PhD at PSU is a renowned expert in stress resilience and recovery and ecological momentary assessment (EMA). [name] collaborates with the UIC team and is responsible for the PSU research team. [name], PhD at WashU brings expertise on Lumen design and development, human-computer interaction, and bioinformatics. [name], PhD at Stanford is an experienced biostatistician and is responsible for developing and executing the statistical analysis plan of this project.

**Informed Consent.** All study participants involved in both the formative research and the pilot RCT must provide eConsent. The eConsent is obtained remotely via telephone or online video conferenced teleorientation session with trained study staff who leads the participant through the consent process and answer any questions about the study. Study personnel obtaining informed consent are experienced in obtaining informed consent and receive standardized training in trial-specific protocols. Risks and benefits and the voluntary nature of the study will be thoroughly explained by the study personnel. The participant will have as much time and information as needed to consider whether or not to participate.

### Aim 1: Formative Research

ENGAGE-2 participants (enrolled but not active in the 2018-1174 protocol) who first screen eligible for access to Lumen compatible Internet-enabled devices, are scheduled for teleorientation with study staff who lead a full informed consent discussion and use the eConsent framework to provide written informed consent documentation (ICD).

### Aim 2: Pilot RCT

The study uses a 2-step consent process, an online screening consent is first obtained prior to initial eligibility screening, which facilitates participant self-screening. Second, screened eligible and interested participants are invited to attend a teleorientation with study staff who lead a full informed consent discussion and use the eConsent framework to provide written informed consent documentation (ICD).

All participants document their consent electronically using the secure REDCap eConsent framework and obtain their pdf copy of the signed consent by directly downloading through REDCap. The study copy is

automatically archived in the file repository in REDCap database, which is a HIPAA-compliant server, accessible to the PIs and study personnel.

**Subject Confidentiality.** See Protection against breaches of participant privacy and confidentiality in Section 7.0.

**Unanticipated Problems.** An unanticipated problem (UP) is defined to include any incident, experience, or outcome that meets all of the following criteria:

- \* Unexpected (in terms of nature, severity, or frequency) given (a) the research procedures that are described in the protocol-related documents, such as the IRB-approved research protocol and informed consent document; and (b) the expected natural progression of any underlying disease, disorder, or condition of the subject experiencing the UP and the subject's predisposing risk factor profile for the UP;
- \* At least possibly related to participation in the research (possibly related means there is a reasonable possibility that the incident, experience, or outcome may have been caused by the procedures involved in the research); and
- \* Suggests that the research places subjects or others at a greater risk of harm (including physical, psychological, economic, or social harm) than was previously known or recognized.

Within 5 business days of the PI learning of a UP or major protocol deviation, the PI informs the Director of IRB panel and all relevant oversight committees at the university. Within 15 business days of the PI becoming aware of non-serious AE, changes in risk/benefit, or events requiring report to the sponsor, these will be reported. An annual report will be submitted to the IRB and the sponsor summarizing all AEs, serious or not.

[figure not shown]
## APPENDICES

### Appendix 1. Design and Training of Lumen and Participant Interaction

#### Section A: Lumen Architecture

Lumen is a voice-only virtual coach that delivers Problem Solving Treatment (PST) to counsel participants with depression and/or anxiety using the 7-step problem solving process and the SSTA (stop, slow down, think and act) method of coping. Lumen conducts interactive conversations providing appropriate responses based on participant input. In order to deliver seamless interactions, we developed a robust and parsimonious architecture that combines PST, integrated components to provide context for Lumen conversations, data storage for the interactions, and a software infrastructure for providing security and privacy for these interactions.

Lumen architecture (see Figure 1) was developed with input and consultation from researchers (in computer science, medicine, health service researchers, and psychiatry), software developers, and human computer interaction experts. The architecture was developed on Amazon's Alexa platform, with further integration with a secure REDCap system for ecological momentary assessments (EMAs) and surveys. Lumen's software architecture comprises of two components: a conversation manager module and a context manager module.

**Figure 1. Lumen software architecture that includes the conversation manager and context manager modules.**

The **conversation manager** is the voice-interactive component of Lumen and is responsible for delivering PST content. This PST content is aligned with the theoretical constructs and associated treatment guidelines. Towards this end, the conversation manager includes a PST engine that incorporates PST-related and conversational structures. The PST engine is a flexible set up that allows for the adaptation of PST content for other health-related problems (e.g., translating the therapy for weight management or smoking cessation) in the future.

Within the Lumen application, the PST engine tracks the progress of a PST session. For example, in a session, once the participant defines a specific problem to work on (step 1), Lumen will proceed to guide the participant in establishing a realistic goal for solving the problem (step 2). Then, once the participant has defined a set of potential solutions that can meet the goal (step 3), Lumen will guide the participant on evaluation of the pros and cons of each solution (step 4). After the participant chooses his/her preferred solution (step 5), Lumen will guide the participant to develop an action plan (step 6), which Lumen will prompt the participant to implement and evaluate the outcome post the session (step 7). This stepwise structure is the same in all PST sessions as is the case in current practice, and the participant identifies the problem in each session (except session 1, which is an introductory overview session situating the PST process). Importantly, each of these steps is based on established PST theory and practice.

In addition, the conversation manager also manages the “state” of the conversation—including the flow of interactive conversation (e.g., the flow of the above-mentioned steps), and adaptive responses based on user input. The conversational state is adaptively managed based on user input. Towards this end, user “intents” or statements are parsed and mapped into pre-defined categories, which are then mapped to the appropriate state in the PST interaction to deliver relevant content, aligned with the user input. The conversation manager also provides dynamic support for functions such as resume, which allows participants to re-start a previously incomplete PST session. Such stop-restart functions provide flexibility in conversational interactions, affording perceptions of realistic conversational interactions.

The conversation manager also interacts with a **context manager** module that provides situated and contextual information regarding Lumen sessions. The context manager primarily controls three aspects: persistence of therapy content across sessions, scheduling/re-scheduling of sessions, and integrating external content (e.g., surveys, EMAs) into the Lumen sessions. The context manager dynamically tracks user problems (see step 1 above), and potential action plans that were previously developed and evaluates adherence to those plans in ensuing sessions. Such dynamic follow-up increases the persistence and continuity of therapy across sessions, developing trust and confidence in the virtual coach. Similarly, the context manager tracks session progress (e.g., session 5), and helps participants schedule and re-schedule sessions. With its integration with an external scheduling database (in REDCap), follow-up emails and messages are tracked to ensure that the therapy sessions are synchronized with participant needs. Finally, the context manager also interacts with the REDCap database to incorporate survey responses (e.g., completion of the PHQ-9 and GAD-7 surveys) into the Lumen session. For example, prior to the start of each Lumen session, participants are asked to complete the PHQ-9 and GAD-7 surveys; if incomplete (or partially complete), Coach Lumen reminds the user to complete the survey prior to re-starting the session. Further, if a user delays session attendance after having completed the surveys, Lumen checks whether a survey is current (within 3 days) to

the session and directs the user to complete an updated survey, if necessary. Additionally, the context manager assures that PST session intervals are maintained by preventing premature session attendance, enabling sessions after 6 days of the last session completed (for sessions 2-4) or after 13 days (for sessions 5-8) for treatment fidelity.

[figure not shown]
All sessions and communicative interactions are stored in a secure AWS-based database for analysis. In order to prevent accidental recording, and for pragmatic implementation in a clinical trial, we currently have implemented the entire Lumen infrastructure in a “locked down” mode iPad. Participants can access the Lumen application skill within the Alexa application by stating “Alexa Open Lumen...” A summary of the Lumen components is provided in Table 1.

**Table 1. Lumen components, and their associated functions.**

Lumen Component	Functions
Conversational manager	Managing conversations based on user intent, aligning with PST constructs, additional functions to manage conversations (e.g., repeat, resume), tracking progress within a session
Context manager	Tracking user problems (from previous PST sessions) and action plans, integrating user responses from PHQ-9 and GAD-7 surveys within sessions, scheduling/re-scheduling sessions,
Lumen REDCap database	Scheduled delivery of Ecological daily assessments, patient surveys, patient calendaring and reminders; Event window checks on session intervals and survey expiration.
Storage/Data Management (AWS & REDCap)	Comprehensive storage of user responses to surveys, user interactions with the Lumen, synchronization across devices, data security and privacy

**Section B: Interacting with Lumen**

Lumen architecture that is presented in Section A, is realized through user interactions with the Lumen skill embedded within the Alexa application (currently delivered on an iPad device) and user completion of surveys and EMAs with hyperlinks delivered via emails and text messages (on the participant mobile phones) (see **Figure 2**).

**Figure 2.** User interaction with Lumen for PST sessions

Participant interaction with the Lumen PST coach involves two primary components: (a) sessions with the coach, and (b) completion of surveys, EMAs, administrative management (e.g., session scheduling, re-scheduling, and monitoring progress).

Participants access their scheduled Lumen session via the Alexa application on their assigned iPad. Sessions are instantiated by the participant by saying “Alexa Open Lumen.” Conversations then continue based on the progress that participants have made (e.g., number of sessions completed), current problem(s) being addressed and implementation of previously created goals and action plans. As previously described, these conversations are aligned with PST’s treatment protocol and guidelines and with conversational structures and flow that reinforce the patient-centered approach of PST. As with regular conversations, participants can exit, resume or ask the Lumen coach to repeat parts of the conversations that they are unable to follow. At the end of each session, participants schedule their next session with Lumen.

Lumen’s PST sessions are delivered on a dedicated iPad, which is encrypted and functions in a “lockdown” mode with no additional functions or local storage. The purpose of using such an approach is for trialing it in a controlled environment without compromising on data safety and privacy of the user. Additionally, such an infrastructure and set-up provide several advantages. First, it creates the perception of a “device as a therapist” mode, assigning a specific role-based purpose (i.e., Lumen as a health coach, that is delivered only on the specific device). Second, embedding the Lumen skill within the Alexa application reduces the potential for accidental recording (as is common with smart speaker devices such as Echo or Google Assistant). Finally, the encrypted mode with no local data storage allows for data privacy protection and remote management, in case of a lost or misplaced device.

Between sessions, participants will also complete surveys and EMAs to track their progress. These administrative tasks and surveys, which provide situated context for Lumen interaction and monitoring of progress will be delivered on the participant's personal devices. The surveys and EMAs are sent as text messages with embedded links. Participants complete these on any browser associated with their mobile phone. Additional messages will include reminders about sessions, ability to schedule/re-schedule planned sessions, and other session related information. All of the survey, EMA and scheduling tasks are instantiated through a dedicated REDCap project. Based on an initial session date a program calendar according to PST guidelines (4 weekly, then 4 biweekly sessions) are set up and used for all session reminders. Future session appointments are confirmed or adjusted per user preference during Lumen sessions and are automatically updated in REDCap to assure that survey are delivered at appropriate times.

## Appendix 2. SPEAC Schedule of Measures – Aim 2 Pilot RCT

Measure	Instrument	Collection Method	Time (weeks) a			
			Screening	0	16	1-12
Eligibility criteria	Age, sex, current/planned pregnancy/lactation, etc.	Self-report	X			
Depression severity	Patient Health Questionnaire-9 (PHQ9), suicidal ideation (item #9)	Self-report	X			
Anxiety	Generalized Anxiety Disorder Scale (GAD7)	Self-report	X			
Alcohol/substance abuse	CAGE Adapted to Include Drugs (CAGE-AID)	Self-report	X			
Brain scan screening	Brain scan screening questions (e.g., self-reported weight)	Self-report	X			
Cognitive Impairment	Callahan 6-item screener	Interview	X			
Emotional reactivity and cognitive control	fMRI	Measured		X	X	NA
Emotional reactivity and cognitive control	Penn State Worry Questionnaire  Positive and Negative Affect Schedule (PANAS) 	self-report		X	X	NA
	Social Problem Solving Inventory-Revised: Short (SPSI-R:S)  Dysfunctional Attitudes Scale 	self-report		X	X	NA
	Depression and anxiety symptoms	Hospital Anxiety and Depression Scale (HADS) 	self-report		X b	X b
Functioning	Sheehan Disability Scale,  Work productivity and activity impairment questionnaire (WPAI) 	self-report		X	X	NA
Quality of life	12-item Short-Form Health Survey (SF12) 	self-report		X	X	NA
Mood	Daily mood (items from circumplex model, capturing affective valence and arousal)	Ecological end-of-day assessments, per Event Window table in Appendix 4.		X	X	X c
Stress	Daily stress events (15 categories), perceived stressor severity, stressor-related thoughts			X	X	X c
Appraisal	Assessing daily implementation of “problem orientation” (challenge appraisals, optimism, self-efficacy, outcome expectancies)			X	X	X c
Coping	Assessing daily implementation of “problem solving-style” (attempts to understand problems, plan effective solutions to coping, impulsivity,			X	X	X c

	carelessness, avoidance behaviors)					
Depression and anxiety symptoms	PHQ9 and GAD7	Self-report and data tracking during PST sessions, per Event Window table in Appendix. 4		X b	NA	X b
Treatment acceptability	Session metrics : Number and duration of PST sessions completed; End-of-session Lumen user survey : NASA Task Load Index (TLX),  User Experience Questionnaire-Short version (UEQ-S),  adapted Working Alliance Inventory for digital interventions (WAI-Tech) 			NA	NA	X
Digital health literacy	Digital Health Literacy Instrument 	self-report		X	NA	NA
COVID impact	COVID impact survey 	self-report		X	NA	NA
Religious involvement	Duke University Religion Index 	Self-report		X	NA	NA
COVID impact on social functioning	COVID impact on social functioning survey	self-report		X	X	NA
Social network	Social Network Index 	Self-report		NA	NA	X
Loneliness	UCLA 3-item loneliness survey 	Self-report		NA	NA	X
Height	Height	Measured		X	NA	NA
Weight	Body weight	Measured		X	X	NA
Blood pressure	Blood pressure	Measured		X	X	NA
Sociodemographics	age, sex, race, ethnicity, education, race, ethnicity, income, household size, marital status, employment status, occupation, smoking/vaping	self-report		X	NA	NA
Adverse Events (AE)	AE form	Interview		X	X	NA

aTo minimize missing data, participants will receive \$50 at wk 0, study iPad (unlocked) or \$100 (if opting out iPad) at wk 16, and \$1 per daily diary.

bHADS is used as the independent outcome measure of depressive and anxiety symptoms at weeks 0 and 16. PHQ9 and GAD7 are used for 2 purposes: (1) eligibility screening (before week 0) and (2) treatment progress monitoring across PST sessions (in weeks 1, 2, 3, 4, 6, 8, 10, 12).

cIn addition to ecological daily assessments that will occur for 7 days at weeks 0 and 16, they also will occur every 2 weeks (on weeks 2, 4, 6, 8, 10, 12). During active treatment in the Lumen arm (Studies 1 & 2) or the in-person PST arm (Study 2), this will occur for 3 days prior to, the day of, and 3 days after each scheduled PST session. For waitlist controls, this will occur for 7 days starting on Sunday of each assigned week.

## Appendix 3. Power analysis and statistical analysis plan – Aim 2 Pilot RCT

### A. Power Analysis

The primary objective of the Pilot RCT in the R61 phase is to evaluate neural target engagement based on the criteria (specified in B.1 below) in order to transition to the R33 phase. Research to examine neural targets as mechanisms of psychotherapy is an emerging field. No prespecified treatment difference of clinical importance or established effect sizes are available for our proposed neural target measures from fMRI. To address such early stage research, Julious recommended that rather than powering in the traditional fashion to test a formal hypothesis of a (in truth unknown) desirable treatment difference, the sample size be selected in order to provide a given level of precision of the treatment effect estimates using the confidence interval (CI) approach, which Ma et al. have used in a completed NIH-funded pilot RCT. Specifically, Julious and others recommended the use of precision intervals of prespecified standardized width to guide sample size determination. Julious offered a further refinement to provide *Assurance* (akin to power) that a chosen standardized width of the precision interval contains the true mean treatment difference. To obtain a precision interval with a 2-sided standardized half-width of 0.5 (akin to a medium effect size) with 90% assurance, we have planned a sample size of 60 ( $n_{Trt}=40$ ,  $n_{Con}=20$ ), assuming  $\geq 85\%$  retention at 16 weeks. This will provide reliable estimates of *meaningful improvement* from week 0 to 16 in amygdala activity for nonconscious threat-related reactivity and in DLPFC activity for cognitive control among Lumen participants, compared with waitlist controls (target engagement criterion (1); see below). Tests of the 2 *a priori* neural targets—amygdala for emotional reactivity and DLPFC for cognitive control—are regarded as separate inferential domains, that is, not within one family of comparisons, and thus are not corrected for multiplicity (or familywise error rate) across domains. Importantly, as explained, the objective of the Pilot RCT is not to claim statistical significance of a prespecified key hypothesis but to obtain reliable effect estimates with precision for a decision on transition to the next phase. In this context, multiple testing is not required or recommended.

For criterion (2), we will examine correlations of change in amygdala activity with change in validated self-report measures of emotional reactivity (affect, worry), and correlations of change in DLPFC activity with change in validated self-report measures of cognitive control (problem solving, dysfunctional attitudes), among Lumen and waitlist participants. A sample size of 60 will be sufficient to detect a correlation coefficient of  $r=0.4$  with 0.80 power and 2-sided  $\alpha=0.05$ . We are not focused on smaller correlations ( $r<0.4$ ) because their implications are likely to have more limited clinical relevance.

### B. Statistical Analysis Plan

#### B.1. Treatment effects on target engagement

Based on literature and our preliminary data, we define neural targets *a priori* as activation of the amygdala for nonconscious threat-related emotion reactivity and activation of the DLPFC for cognitive control. The activation variables are from fMRI, which will be completed at weeks 0 and 16. Also, validated self-report surveys of emotional reactivity (worry, affect) and cognitive control (problem solving, dysfunctional attitudes) will be obtained at weeks 0 and 16. These self-report measures were chosen because of prior evidence for their role mediating the effect of PST on depressive symptoms.

Note that improvement for emotional reactivity corresponds to a *decrease* in amygdala activity whereas improvement for cognitive control corresponds to an *increase* in DLPFC activity. For consistency in the presentation of analyses, the measure will be constructed such that higher positive values are better; thus, change toward a *higher value is improvement*.

Activation of either neural target satisfies 2 criteria:

- i. Criterion 1. The level of task-evoked activation for either the amygdala for nonconscious threat-related emotional reactivity or for the DLPFC for cognitive control improves meaningfully from week 0 to 16 in the Lumen group compared with the waitlist control group.

The ENGAGE Phase 1 project (UIC IRB protocol #2015-1324) showed significant improvement in amygdala activation for nonconscious threat-related emotional reactivity from baseline to 2 months, and the standardized treatment effect was Cohen's  $d=0.6$ . We also underscore that the 2-month time point in that project, which tested an integrated depression and obesity behavioral treatment, coincided with the start of weight loss treatment, which was sequenced after the first 5 PST sessions for depression, so measurements of neural targets at 2 months assessed the effect of PST alone. In ENGAGE, PST was delivered via in-person individual sessions with trained coaches.

The SPEAC project is at the frontier of research on developing a voice-based AI agent (Lumen) for PST and validating its effect on *a priori* neural targets, and the Pilot RCT (Study 1) is to estimate possible effects of target engagement, which, if promising, will support further investigation to confirm target engagement in Study 2. In this context, we apply a precision interval approach (see Section A above) to determine Criterion 1. We define that, compared with the waitlist control group, the Lumen PST treatment group will demonstrate a *meaningful improvement* in a neural target if the standardized between-group mean difference is at least Cohen's  $d=0.3$  in favor of Lumen (small effect; 50% of that in ENGAGE). At this effect size, the upper limit of the precision interval overlaps with  $d=0.8$  (large effect) given a standardized half-width of 0.5 with 90% assurance that the interval contains the true mean difference based on the power analysis. We consider such a finding to be meaningful and will suffice Criterion 1.

- ii. Criterion 2. Change in the level of task-evoked activation of a neural target that meets Criterion 1 correlates with temporally concurrent change from week 0 to 16 in self-reported measures within the corresponding PST theory-based construct for emotional reactivity or cognitive control. As noted, we consider correlations of  $r=0.4$  or greater meaningful. Specifically:
  - a. If the amygdala target exhibits a meaningful improvement in the Lumen group vs. the waitlist control (Criterion 1), then we will examine whether that improvement is significantly correlated with improvements in validated self-report measures of emotional reactivity (worry, affect) over the same 0-to-16-week interval.
  - b. If the DLPFC target exhibits a meaningful improvement in the Lumen group vs. the waitlist control (Criterion 1), then we will examine whether that improvement is significantly correlated with improvements in cognitive control (problem solving, dysfunctional attitudes) over the same 0-to-16-week interval.

Criterion 1 is tested via *t* test that compares the change from week 0 to 16 in the Lumen group with that change in the waitlist control group. Participants are analyzed based on the group to which they are assigned using all available data. The *t* test described above can be readily expanded for exploratory subgroup analyses by applying to each subgroup (e.g., female vs. male).

To test Criterion 2, we will examine the regression change of the amygdala activity from week 0 to 16 on change in self-reported measures of emotional reactivity (worry, affect) from week 0 to 16, controlling for baseline values of the self-reported measures and group assignment. We expect that the coefficient for the change in amygdala activation is significant and positive in the direction of improvement in its corresponding, validated emotional reactivity self-report measures and that this relationship may be significantly modified by group assignment. Similarly, we will examine the regression change of the DLPFC activity from week 0 to 16 on change in self-reported measures of cognitive control (problem

solving, dysfunctional attitudes) from week 0 to 16, controlling for baseline values of the self-reported measures and group assignment. We expect that the coefficient for the change in DLPFC activation is significant and positive in the direction of improvement in its corresponding, cognitive control validated self-report measures and that this relationship may be significantly modified by group assignment.

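### Does naming both a d ≥ 0.3 cut-off and a t test without an alpha leave Criterion 1 with two competing rules?

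*Combined protocol and SAP*

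**What the plan says.** Appendix 3, B.1 introduces the rule with "In this context, we apply a precision interval approach (see Section A above) to determine Criterion 1". It defines meaningful improvement as a standardized between-group difference of at least d = 0.3 in favour of Lumen, which is half the d = 0.6 seen in the earlier ENGAGE project, and adds "We consider such a finding to be meaningful and will suffice Criterion 1". It describes the interval as "given a standardized half-width of 0.5 with 90% assurance that the interval contains the true mean difference based on the power analysis". Further down, the analysis is given as a t "test that compares the change from week 0 to 16 in the Lumen group with that change in the waitlist control group".

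Appendix 3, A (Power Analysis) gives the basis for N = 60 (40 v 20, at least 85% retention): "To obtain a precision interval with a 2-sided standardized half-width of 0.5 (akin to a medium effect size) with 90% assurance". It glosses assurance as "akin to power) that a chosen standardized width of the precision interval contains the true mean treatment difference". It also says that "the objective of the Pilot RCT is not to claim statistical significance of a prespecified key hypothesis", and that the decision to move to the next phase rests on effect estimates of adequate precision.

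Section 9.0 (Aim 2) repeats the t test and the requirement of a meaningful improvement but not the 0.3 cut-off. It ends by sending the reader to Appendix 3 for the detailed analysis plan.

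**The concern.** Three features invite doubt.

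- B.1 attaches both a cut-off on the estimate and a t test to Criterion 1 and does not say what the test decides. A reader used to confirmatory trials may take the test to mean p < 0.05.
- Section 9.0, read alone, shows only the test.
- The 90% is likened to power, so it could be taken as a probability of attaining a given width rather than as a confidence level. An analyst might then report a 95% interval by habit. B.1 also mentions only the upper end of the interval at d = 0.3, namely 0.8.

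Criterion 2 is examined only for a target that passes Criterion 1, and both feed the decision to move to the R33 phase. If two rules were truly open, the choice between them could be made after the data were seen.

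**Working it through.** **Inputs.** From the documents: 40 v 20 randomized and at least 85% retention (section 9.0; Appendix 3, A); half-width 0.5 and 90% assurance (Appendix 3, A); cut-off d = 0.3 and earlier effect d = 0.6 (Appendix 3, B.1). Assumed: exactly 85% retention in each arm, giving 34 v 17; normal change scores; d in pooled SDs of change. No alpha is given for Criterion 1, so two-sided 0.05 and 0.10 are both shown. The only stated alpha, two-sided 0.05, belongs to the Criterion 2 correlation.

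**1. The planned sample size.** Half-width = t(0.95; n1+n2−2) × √(1/n1 + 1/n2).
- √(1/34 + 1/17) = 0.2970, df = 49, t = 1.677, so the half-width is 0.498.
- 51 is the smallest 2:1 number of completers that gives 0.5 or less, and 51/0.85 = 60. The planned N reproduces exactly.
- At d = 0.3 this interval runs from −0.20 to 0.80. Its upper end is the 0.8 quoted in B.1.
- A two-sided 95% interval has half-width 2.010 × 0.2970 = 0.597. It would run from about −0.30 to 0.90 and would not match that 0.8.

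So the 90% works as an ordinary two-sided confidence level. That is also how both sections word it, since each speaks of the interval containing the true difference.

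**2. Where a cut-off and a test would disagree.** The smallest observed d that reaches significance is the critical t × √(1/n1 + 1/n2).

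| Completers | Two-sided alpha | Critical d | Zone of disagreement |
|---|---|---|---|
| 34 v 17 | 0.05 | 2.010 × 0.2970 = 0.597 | 0.30 to just under 0.60 |
| 34 v 17 | 0.10 | 1.677 × 0.2970 = 0.498 | 0.30 to just under 0.50 |
| 40 v 20 | 0.05 | 2.002 × 0.2739 = 0.548 | 0.30 to just under 0.55 |

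At 34 v 17, d = 0.30 gives t = 0.30/0.2970 = 1.01 and p = 0.32. At d = 0.60, p = 0.049, so the two would agree there at 0.05.

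**3. How often they would disagree** (34 v 17, one target, from the central and noncentral t; significance counted only in favour of Lumen). Disagreement is the first probability minus the second or third.

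| True d | P(observed d ≥ 0.3) | P(p < 0.05) | P(p < 0.10) | Disagree at 0.05 | Disagree at 0.10 |
|---|---|---|---|---|---|
| 0 | 15.9% | 2.5% | 5.0% | 13% | 11% |
| 0.3 | 50.2% | 16.6% | 25.8% | 34% | 24% |
| 0.6 | 84.4% | 50.8% | 63.6% | 34% | 21% |

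**4. Which rule the text selects.** The passages, side by side:
- B.1 gives the d = 0.3 cut-off as the definition of meaningful improvement and says that it is enough.
- The two conditional statements that lead from Criterion 1 to Criterion 2 (B.1, ii, a and b) reuse that defined term and mention no p value.
- Section 3.0 (Aim 2) asks that the target improve meaningfully, but that the correlation be significant. B.1 keeps the same contrast. Where significance is needed, the authors say so.
- Appendix 3, A says that the pilot does not set out to claim significance and that the transition decision rests on estimates.

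All four point to d ≥ 0.3 as the rule. The t test is then the method of comparison that supplies the estimate and its standard error.

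**The case for a change.** The strongest case for a change is that no sentence says outright that the p value does not count. The power section describes the pilot's objective rather than the rule for each criterion, and significance does operate in Criterion 2, within the same decision. A result such as d = 0.45 lies in the zone of disagreement at 34 v 17 and two-sided 0.05, and a clarifying sentence would cost little.

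Some of this stands. The t test does lack an alpha, a sidedness and a stated role; the comparison with power is loose; and the interval carries no plain label. But the t test has no alpha because it is not used to pass or fail anything. To read it as the rule, one must bring in an alpha from Criterion 2 and set aside the sentence saying that the cut-off suffices. Section 9.0 does not offer a rival rule either, since it leaves the detail to Appendix 3. A sentence stating that the cut-off decides would lead the analyst to the same decision as the present text.

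**Conclusion.** The concern does not call for a change. Read as a whole, the plan has one rule for Criterion 1, observed d ≥ 0.3 in favour of Lumen, and one interval, a two-sided 90% interval with planned half-width 0.498 at 34 v 17. Sample size, cut-off and t test are consistent with one another. What is missing is the stated role of the test and a label for the interval, and an analyst who follows Appendix 3 will fill both sensibly.

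The disagreement rates of about one trial in three (34% at a true d of 0.3 or 0.6, two-sided 0.05) or 21-24% (two-sided 0.10) measure the effect of a misreading, not of the plan. They rest on an alpha that the documents do not give for Criterion 1, on equal 85% retention in each arm and on normal change scores. They are rates for one target on Criterion 1 alone and say nothing about the overall transition decision, which also depends on Criterion 2 and the other Phase 1 milestones.
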